**Table 11 Time Schedule – Second day of V6 (Day 30)**

Time	Blood Sample	Procedures	Additional Information
Start of Procedure	Day 30		
Prior to product use	✓	Blood sampling for CYP2A6 assessment	
Prior to breakfast/snack	✓	Blood sampling for biobanking	After at least 6 hours of fasting.
Prior to breakfast/snack	✓	Clinical laboratory parameters (hematology, clinical chemistry)  Collection of spot urine for: - Urinalysis safety panel - Biobanking	After at least 6 hours of fasting.
At least 1h prior to start of product use		Light snack	e.g. biscuit, zwieback, fruit After biobanking blood sampling
Prior to product use		Vital signs	At least 5 min in supine position prior to measurement.
Prior to product use (within 2 hours)		Weighing of product	
Prior to product use	✓	Blood sampling for baseline nicotine level	Prior to T 0 blood will be drawn at the following timepoints:

**Confidentiality Statement**

Data and information contained in this document are considered to constitute trade secrets and confidential commercial information, and the legal protections provided to such trade secrets and confidential information are hereby claimed under the provisions of applicable law. No part of this document may be publicly disclosed without the written consent of Philip Morris Products S.A.

Time	Blood Sample	Procedures	Additional Information
Start of Procedure		Day 30	
10 ± 2 min prior to T 0		VAS-craving: baseline	1 hour ± 5 min before T 0 , 30 min ± 5 min before T 0 , 5 min ± 2 min before T 0 .
Just before T 0		Piercing of P3P capsule	
Start of product use = T 0		Product use	Single product for a duration of up to 15 minutes.
During/after product use	✓	Blood sampling for nicotine PK assessment	Post T 0 , blood will be drawn at the following time points: 4 minutes ± 1 minute after T 0 , 7 minutes ± 1 minute after T 0 , 10 minutes ± 1 minute after T 0 , 15 minutes ± 2 minutes after T 0 , 30 minutes ± 2 minutes after T 0 , 1 hour ± 5 minutes after T 0 , 2 hours ± 5 minutes after T 0 , 4 hours ± 5 minutes after T 0 .
During/after product use		VAS-craving	Post T 0 , craving will be assessed at the following time points: 4 minutes (± 2 minutes) 10 minutes (± 2 minutes) 15 minutes (± 2 minutes) 30 minutes (± 5 minutes) 1 hour (± 10 minutes) 2 hours (± 10 minutes) 4 hours (± 10 minutes)
During product use		Puffing/inhalation behavior question	Assessment performed by site staff.
Within 60 min after product use		Collection and weighing of used product	
Within 60 min after product use		Questionnaires: - ABOUT™-product experience - Product acceptance - Sensory - ABOUT™-dependence	
1 to 2 hours after T 0		Breakfast	

**Confidentiality Statement**

Data and information contained in this document are considered to constitute trade secrets and confidential commercial information, and the legal protections provided to such trade secrets and confidential information are hereby claimed under the provisions of applicable law. No part of this document may be publicly disclosed without the written consent of Philip Morris Products S.A.

Time	Blood Sample	Procedures	Additional Information
Start of Procedure		Day 30	
Shortly before discharge		Vital signs	At least 5 min in supine position prior to measurement. At least 15 min after P3P use
		ECG	After resting for at least 10 min in supine position prior to recording.
		Physical examination	
		Body Weight	
		Spirometry	After resting in sitting position for at least 15 minutes. At least 1 h after P3P use. To be done after vital signs and ECG
During the visit		AE/SAE, concomitant medication recording	
During the visit		Product events malfunctions/misuse	

**Abbreviations:** ABOUT = Assessment of behavioral outcomes related to tobacco and nicotine products; AE = Adverse event; ECG = Electrocardiogram; min = minutes; PK = Pharmacokinetic; SAE = Serious adverse event; VAS = Visual analogue scale

## 9.4 Safety Follow-Up Period

After Discharge on Day 30 or at the time of early discontinuation all enrolled subjects will enter a 14-day Safety Follow-Up Period during which new AE/ will be collected and ongoing AEs/SAEs will be followed-up by the site. The follow-up of ongoing AEs/SAEs will be conducted by the study investigational site as described in sections [8.2.2](#) and [8.2.6](#).

## 9.5 Early Termination Procedures

If a subject is discontinued from the study, all early termination procedures listed below are performed unless the subject refuses to perform the assessments.

**Table 12 Time Schedule – Early Termination**

Blood Sample	Procedures	Additional Information
	Return of used and unused P3P consumables	
✓	Clinical laboratory parameters (hematology, clinical chemistry)	May be done in non-fasting state.
	Urine analysis safety panel	
	Urine pregnancy test (all female subjects)	
	Vital signs (blood pressure, pulse rate, respiratory rate)	At least 5 min in supine position prior to measurement. At least 15 min after P3P use
	ECG	After resting for at least 10 min in supine position prior to recording.
	Spirometry	After resting in sitting position for at least 15 minutes. At least 1 h after P3P use. To be done after vital signs and ECG.
	Physical examination	
	Information on risks of smoking, smoking cessation advice	
	Concomitant disease status check	Provide stop date if available or note ongoing if ongoing at early termination
	AE/SAE, concomitant medication recording	
	Product events malfunctions/misuse	
	Discharge	

Abbreviations: AE = Adverse event; ECG = Electrocardiogram; SAE = Serious adverse event

If a subject withdraws from the study or is discontinued during a planned visit, assessments required as per protocol for early termination that have been already performed during the planned visit should not be conducted again.

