### **The Admission Visit (V2 [Day -1])**

At V2, subjects will return to the investigational site for Admission (Day -1). Subjects should have been fasting for at least 6 hours prior to Admission. After confirmation of eligibility, subjects will be enrolled and will undergo baseline assessments. All subjects that are not enrolled will be considered as screen failures. At Admission, enrolled subjects will perform a product test using up to 6 P3P products (alternating between P3P-1mg and P3P-2mg). In order to continue in the study, each subject will need to test at least one product of each P3P variant during the product test. Subjects should be abstinent from the use of any tobacco/nicotine containing products for at least 4 hours prior to product test. After the product test, subjects not willing and/or not ready to use P3P will be discontinued from the study and will undertake early termination procedures on the same day (section 9.5) and will enter the 14-day Safety Follow-Up Period. Subjects willing and ready to use P3P during the study will be randomized either to P3P-1mg or P3P-2mg in a 1:1 ratio and will start their first overnight (confinement) period for pharmacokinetics assessments on Day 1. The subjects and the Investigator will be blinded to the randomization arm.

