## 5.2 Discontinuation of Subjects from the Study

Discontinued subjects will include both subjects who withdraw from the study (subject's decision) or subjects who are discontinued from the study by the decision of the Investigator. A subject can only be discontinued from the study after enrollment.

Subjects will be informed that they are free to withdraw from the study at any time. Subjects will be questioned for the reason for withdrawal from the study, although they are not obliged to disclose it. If the subject withdraws from the study, he/she will be asked to confirm that he/she agrees to undertake the early termination procedures for safety assessments, and this information will be fully documented by Investigator.

The subject will be informed that if he/she withdraws from the study, the data collected until the point of withdrawal will be maintained as part of the study data. The samples collected prior to withdrawal will be analyzed, even after his/her withdrawal unless the subject confirms his/her disagreement to the site staff and the disagreement is documented.

When a subject is discontinued from the study, all early termination procedures (section 9.5) will be performed unless the subject refuses to perform the assessments. Early termination procedures are to be performed only for subjects who have been exposed to P3P. Early termination visit should be performed within 7 days from the date of discontinuation. After the date of termination, the subject will enter into the 14-day Safety Follow-Up Period. This applies to all subjects independent of the reason of discontinuation (for example, withdrawal of consent, or at the Investigator's decision etc).

Subjects must be discontinued from the study for any of the following reasons:

- Withdrawal of informed consent.

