### Confidentiality Statement

Data and information contained in this document are considered to constitute trade secrets and confidential commercial information, and the legal protections provided to such trade secrets and confidential information are hereby claimed under the provisions of applicable law. No part of this document may be publicly disclosed without the written consent of Philip Morris Products S.A.

- Any AE/SAE or condition (including clinically significant changes in a laboratory parameter), which at the discretion of the Investigator no longer justifies the subject's participation in this study.
- Positive pregnancy test (section 8.5).
- The Sponsor or Investigator terminates the study or the study terminates at a particular investigational site. If the Sponsor or the Investigator decides to prematurely terminate the study, the subject will be promptly informed. The head of the investigational site should report the fact and the reason in writing to the IEC.
- Discontinuation is considered to be in the best interest of the subject or the other subjects as judged by the Investigator.
- Subject is not willing to use P3P after the product test at Admission. In such a situation, the subject will be discontinued immediately after the product test.

Subjects may be discontinued from the study for the following reason:

- Non-compliance with the study procedures based on the judgment of the Investigator.

Use of any tobacco and nicotine containing product other than P3P during the ambulatory exposure period will not lead to the discontinuation of the subject from the study. However, the subjects will be instructed to use exclusively P3P (up to 15 products daily) during this period. Until randomization subjects can be replaced, however subjects that discontinue the study after randomization will not be replaced.

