## 9.2 Admission Visit

Visit 2 will consist of 3 consecutive days (Day -1, Day 1 and Day 2) with on-site overnight period. Admission, enrollment, product test and randomization will take place at the first day of the visit (Day -1) while nicotine PK will be assessed on the second day of the visit (Day 1), after an overnight nicotine abstinence period of at least 10 hours. Following the PK assessments, subjects will remain on-site and will be allowed to use up to 15 P3P products daily on Day 1 and Day 2. The assessments performed at the first day of V2 (Day -1) are listed in [Table 6](#); the assessments performed at the second day of V2 (Day 1) are listed in [Table 7](#) and the assessments performed at the third day of V2 (Day 2) are listed in [Table 8](#).

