**Table 6 Time Schedule – First day of V2 (Day -1)**

Time	Blood Sample	Procedures	Additional Information
Start of Procedure	Day -1		
Before enrollment		Concomitant medication Collection of spot urine for: - Urine drug screen - Urine cotinine screen - Pregnancy test (all female subjects) Alcohol breath test Review of Inclusion criteria 4, 5 and 7 and exclusion criteria 11, 13, 14 and 19	
Before enrollment		Information on risks of smoking, smoking cessation advice and product debrief	
Enrollment		Enrollment	
After enrollment, before product test	✓	Clinical laboratory parameters (hematology, clinical chemistry) Collection of spot urine for: - Urinalysis safety panel - BoExp and creatinine Physical examination Vital signs	After at least 6 hours of fasting. At least 5 min in supine position prior to measurement. At least 15 minutes smoking abstinence prior to measurement.

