12.1.3 Descriptive Statistics

All data will be presented in listings.

All endpoints will be summarized with descriptive statistics including number of subjects (n), number and percent of subjects with missing data, arithmetic means, 95% confidence intervals of the mean, and standard deviations (SD), median, first and third quartiles, minimum and maximum. Change from baseline will be added to the summary statistics when applicable.

For log normally distributed endpoints geometric mean, 95% confidence intervals of the geometric mean, geometric CV will be presented instead of arithmetic mean, 95% confidence intervals of the mean, and SD and percent change from baseline will be presented instead of change from baseline.

Categorical variables will be summarized by frequency statistics (number and percentage). For endpoints relating to sampling times (e.g., tmax) only median, first and third quartiles, and minimum and maximum will be presented.

Summary statistics and statistical analyses will be performed for subjects included in the relevant analysis population. For the calculation of summary statistics and statistical analysis, unrounded data will be used.

Summaries on Safety population will be produced by randomization group and overall, including the available data from subjects who tested the product but were not randomized.

The following product labels and descriptions will be used for the TFLs (Table 12):

Table 12: Product Labels

Randomization Group/P3P Variant	Format used in TFLs	Order in TFLs
P3P-1mg	P3P-1mg	1

P3P-2mgP3P-2mg

2

The following stratification labels (Table 13) for the TFLs will be used:

Table 13: Stratification Labels

Stratification Factor	
Sex	Male
	Female
Product Exposure Category	≤ 5 P3P/Day
	>5-10 P3P/Day
	>10 P3P/Day

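### The early-termination skip rule in protocol section 9.5 lets pre-exposure Day -1 results stand in for the post-exposure ECG, laboratory panel and urinalysis when a subject stops during V2

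*Protocol*

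**What the plan says.** Protocol section 9.5 first calls for the whole Table 12 set, which includes the laboratory panel, urinalysis, vital signs, ECG, spirometry and physical examination, unless the subject refuses. The sentence after Table 12 then makes an exception for a subject who stops partway through a scheduled visit: "assessments required as per protocol for early termination that have been already performed during the planned visit should not be conducted again". It sets no condition on timing relative to P3P use.

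Section 5.2 defines who is covered: "Early termination procedures are to be performed only for subjects who have been exposed to P3P". For a subject unwilling to go on after the product test, the same section says that "the subject will be discontinued immediately after the product test", and section 4.1 places the early-termination procedures on that same day.

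Section 9.2 defines the visit: "Visit 2 will consist of 3 consecutive days (Day -1, Day 1 and Day 2) with on-site overnight period". Table 6 puts the Day -1 laboratory panel, urinalysis, physical examination, ECG, first vital signs and first spirometry in the block labelled "After enrollment, before product test".

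On the analysis side, protocol section 12.1.2 takes the last pre-test value as the safety baseline, and section 12.3.1 puts anyone exposed in the product test into the safety population if they have a safety assessment. The SAP, section 12.1.3, summarizes that population "including the available data from subjects who tested the product but were not randomized". SAP section 12.5.9.4 reports laboratory data at Day 30 or early termination, with changes from baseline.

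**The concern.** Early-termination procedures are reserved for people who have used the product, so their evident purpose is a check after exposure. A rule against repeating tests within a visit saves burden and is harmless when the earlier test also followed exposure. V2 is the one visit where that fails: it starts before any P3P use, and three of its safety assessments are placed ahead of the first use.

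Changes from baseline in ECG and laboratory values are listed safety endpoints. For a subject who stops during V2, the Day -1 laboratory result is already the baseline. If it also serves as the early-termination value, the change is zero by construction; if it does not, the value is missing. Subjects who leave because they tolerate the inhaled powder poorly are among those affected, so the summaries could lean towards subjects who tolerated it.

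**Working it through.** The plan gives no figure for this point, so the check is to lay the schedule beside the skip rule.

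**Step 1: how many laboratory draws does V2 contain?** Section 7.5.1 schedules the panel at V1, V2, V4 and V6. Section 7.6.1 gives 20 mL per safety draw and about 80 mL in total: 4 × 20 = 80 mL. The overall volume also agrees: 99 + 8 + 5 + 80 + 46 = 238 mL. V2 therefore has one draw, and Table 6 places it before the product test. Tables 7 and 8 list neither a laboratory panel nor a urinalysis.

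**Step 2: what post-exposure results exist, by time of stopping, if the rule is read literally?** Sources: Tables 6 to 8, sections 7.3.5, 7.3.7 and 7.3.9, and Appendix A footnotes c and e.

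| Subject stops | ECG | Laboratory panel | Urinalysis | Physical examination | Vital signs | Spirometry |
|---|---|---|---|---|---|---|
| Day -1, after product test | 0 | 0 | 0 | Section 7.3.5 plans one before V2 discharge; none listed in Table 6 | Planned; Table 6 row sits below Randomization | Planned; Table 6 row sits below Randomization |
| Day 1, before end-of-day checks | 0 | 0 | 0 | As above; none listed in Table 7 | Day -1 post-test and Day 1 morning | Day -1 post-test and Day 1 morning; none after the randomized product |
| Day 2, before discharge checks | 1 (end of Day 1) | 0 | 0 | Section 7.3.5 and Table 8 place it before discharge | Present | Present |
| After V2 discharge, between visits | Full Table 12 set within 7 days (section 5.2) | same | same | same | same | same |

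**Step 3: does the 7-day allowance close the gap within V2?** Not on the wording. The skip rule applies whenever the subject stops during a planned visit, and section 4.1 fixes same-day procedures for those who stop after the product test.

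**Step 4: how many subjects and how much exposure?** The documents give no decline rate. If a fraction d of tested subjects decline and 60 are randomized, the number of decliners is 60/(1 - d) - 60. With d = 0.10 this is 66.7 - 60 = 6.7, about 7. With d = 0.30 it is 85.7 - 60 = 25.7, about 26. Both rates are assumptions. The largest labelled nicotine content in the product test is 3 × 1 mg + 3 × 2 mg = 9 mg. Continuing in the study requires only one product of each variant, 1 + 2 = 3 mg, and a decliner may have used less.

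**The case against.** The strongest reply is that much of the post-exposure check survives. Section 7.3.7 requires Day -1 vital signs before use and again at the end of the day or at discharge. Section 7.3.9 and footnote e schedule spirometry after the product test. Neither is limited to randomized subjects, and Table 12 times both relative to P3P use, so a pre-test reading is hard to pass off as that assessment. Section 7.3.5 plans a physical examination before V2 discharge. Adverse events are recorded on Day -1, followed for 14 days, and are the primary safety assessment (section 12.6.3). All of this stands.

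A reader might infer that every Day -1 assessment counts as already performed, so that a decliner leaves with no post-exposure data and a reaction goes unrecorded. The documents do not support that, for the reasons just given. What remains open is narrower: Table 6 lists the post-test vital signs and spirometry below the Randomization row and no physical examination before a Day -1 discharge.

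A reader might also see sections 5.2 and 9.5 as flatly contradictory. They are not: one says who has the procedures, the other avoids duplicates, and both can be obeyed. Obeying both, however, leaves the same-day check in section 4.1 without an ECG, laboratory panel or urinalysis after exposure.

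It is also fair that decliners, never randomized, can enter only the overall columns; that a laboratory panel repeated within hours may tell little; and that nothing forbids unscheduled tests.

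**Conclusion.** The point holds in limited form. As written, the plan requires no post-exposure ECG for a subject who stops after the product test or on Day 1 before the end-of-day checks, and no post-exposure laboratory panel or urinalysis for any subject who stops before V2 discharge. The ECG gap closes at the end of Day 1. Subjects who stop between visits after V2 discharge get the full set.

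For post-test vital signs, spirometry and physical examination, the problem is only that the text and Table 6 do not say the same thing about decliners.

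The conclusion rests on reading the skip rule literally and V2 as one visit; it does not depend on the decliner count. The range of 7 to 26 is an illustration under assumed rates, and 9 mg is the labelled maximum, not the expected exposure. The effect on the randomized comparison is small. This is a cheap improvement to safety data, not a threat to the primary objective.

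**What to change.** Reconcile protocol sections 4.1, 5.2, 7.3.5, 7.3.7, 7.3.9 and 9.5 with Table 6:

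- In section 9.5, state that an assessment counts as already performed only if it was done after the subject's last P3P use. The same-day Day -1 laboratory panel may stay waived if it is judged uninformative; if so, say so.
- In Table 6, note that the post-test vital signs and spirometry rows apply to all tested subjects, including those not randomized, and make explicit whether the pre-discharge physical examination applies to a Day -1 discharge.

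The cost is one sentence in section 9.5 and a note in Table 6. No procedure is added beyond those in Table 12. Decliners stay somewhat longer, since Table 12 places spirometry at least 1 hour after P3P use. At other visits the condition could occasionally call for a repeat if the subject used P3P between an assessment and stopping.

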## 10 QUALITY CONTROL AND QUALITY ASSURANCE

### 10.1 Monitoring

A Clinical Research Associate (“Monitor”) of the contract research organization (CRO) will be responsible for the monitoring of the study. Monitoring will be performed according to the CRO’s SOPs and as per monitoring plan agreed with the Sponsor.

An Investigator’s meeting will be held prior to the site initiation visit. During this meeting, the general training of the study procedures and specific training on selected procedures will be completed and documented.

Subsequent to the Investigator’s meeting, and before the first subject is screened into the study, the site initiation visit will be conducted by the Monitor and, if necessary, together with the Sponsor or its authorized representative. The purpose of the site initiation visit is described in the monitoring plan.

During the study, the Monitor will have regular contact with the investigational site, including routine monitoring visits. The frequency and purpose of the monitoring visits will be defined in the monitoring plan agreed with the Sponsor.

The Investigator or designee shall permit the Monitor to review study data as frequently as deemed necessary to ensure that data are being recorded in an adequate manner and that protocol adherence is satisfactory.

The Investigator or designee shall access medical records for the Monitor so that entries in the CRFs may be verified. The Investigator and designees, as part of their responsibilities, is expected to ensure that the study adheres to GCP requirements.

The Investigator, or a designated member of the Investigator’s staff, must be available during the monitoring visit to review the data and resolve any queries and to allow direct access to the subject’s records for source data verification.

The Monitor and the Sponsor’s personnel will be available between visits, should the Investigator or other staff at the investigational site need information and/or advice.

Communication by telephone, mail and e-mail may be used as needed to supplement investigational site visits. The Investigator and study personnel will cooperate with the Monitor, provide all appropriate documentation and will be available to discuss the study.

